## **4. PATIENT SELECTION AND RESTRICTIONS**

Investigators should select patients who meet all of the inclusion criteria and none of the exclusion criteria for this study. Investigators should keep a record ie, patient screening log, of patients who entered pre-study screening.

### **4.1 Inclusion criteria**

Patients must meet all of the following criteria:

1. Provision of signed and dated, written informed consent prior to any study specific procedures, assessments, sampling and analyses.  
If a patient declines to participate in any voluntary exploratory research component of the study, there will be no penalty or loss of benefit to the patient and he/she will not be excluded from other aspects of the study
2. Japanese men or women at least 20 years of age
3. Histological or cytological confirmation of a solid, malignant tumour excluding lymphoma that is refractory to standard therapies or for which no standard therapies exist
4. WHO performance status 0-2 with no deterioration over the previous 2 weeks
5. Minimum life expectancy of 16 weeks
6. At least one lesion (measurable and/or non-measurable) that can be accurately assessed at baseline by either CT, magnetic resonance imaging (MRI) or plain X-ray and is suitable for repeated assessment
7. Females should be using adequate contraceptive measures (see Section 4.3), should not be breast feeding and must have a negative pregnancy test prior to start of dosing if of child-bearing potential

OR

Females must have evidence of non-child-bearing potential by fulfilling one of the following criteria at screening:

- Post-menopausal defined as aged more than 50 years and amenorrhoeic for at least 12 months following last menses or cessation of all exogenous hormonal treatments
- Documentation of irreversible surgical sterilisation by hysterectomy, bilateral oophorectomy or bilateral salpingectomy but not tubal ligation

Date

8. Male patients should be willing to use barrier contraception ie, condoms for specified period ( See Section 4.3)
9. Patients should be willing to remain in hospital for at least 1 week after starting on study treatment

## 4.2 Exclusion criteria

Patients must have none of the following:

1. Treatment with any of the following:
  - Nitrosourea or mitomycin C within 6 weeks of the first dose of MEDI-573
  - Any investigational agents or investigational products from a previous clinical study within 30 days of the first dose of MEDI-573, or in the case of monoclonal antibodies, within 6 weeks prior to the first dose of MEDI-573
  - Receipt of any systemic chemotherapy, small molecule targeted therapy (eg, sorafenib or other tyrosine kinase inhibitors) or hormonal therapy for cancer related treatment within 4 weeks of the first dose of MEDI-573
  - Receipt of any biological or immunological based therapies (including, but not limited to, mAb therapy such as bevacizumab or cancer vaccine therapies) within 6 weeks prior to the first dose of MEDI-573
  - Use of immunosuppressive medication other than steroids within 7 days before the first dose of MEDI-573
  - Use of systemic steroids within 7 days before the first dose of MEDI-573 (inhaled and topical corticosteroids are permitted). Patients may take replacement doses of steroids (defined as  $\leq 30$  mg/day hydrocortisone or the equivalent) if on a stable dose for at least 2 weeks prior to the first dose of MEDI-573
  - Previous therapy with medication against IGF (ie, monoclonal antibodies with IGF-IR or IGF-targeting tyrosine kinase inhibitors)
  - MEDI-573 in the present study (ie, dosing with MEDI-573 previously initiated in this study)
  - Major surgery (excluding placement of vascular access) within 4 weeks of the first dose of MEDI-573
  - Radiotherapy with a wide field of radiation within 4 weeks or radiotherapy with a limited field of radiation for palliation within 2 weeks of the first dose of MEDI-573

Date

2. With the exception of alopecia, any unresolved toxicities from prior to cancer therapy greater than CTCAE grade 1 at the time of starting MEDI-573
3. Spinal cord compression or brain metastases unless asymptomatic, treated and stable and not requiring steroids for at least 4 weeks prior to start of MEDI-573
4. As judged by the investigators, any evidence of severe or uncontrolled systemic diseases, including uncontrolled hypertension, active bleeding diatheses, or active infection including hepatitis B, hepatitis C and human immunodeficiency virus (HIV). Screening for chronic conditions is not required
5. Any of the following cardiac criteria:
  - Clinically significant abnormality on electrocardiogram (ECG) (Mean resting corrected QT interval (QTcF) >470 msec obtained from 3 ECGs)
  - New York Heart Association Grade  $\geq 2$  congestive heart failure
  - History of myocardial infarction or unstable angina within 6 months prior to the first dose of MEDI-573
6. History of transient ischemic attack or stroke within 6 months prior to the first dose of MEDI-573
7. Inadequate bone marrow reserve or organ function as demonstrated by any of the following laboratory values:
  - Absolute neutrophil count  $< 1.5 \times 10^9/L$
  - Platelet count  $< 100 \times 10^9/L$
  - Haemoglobin  $< 90 \text{ g/L}$  ( $< 9 \text{ g/dL}$ )
  - Alanine aminotransferase (ALT) and Aspartate aminotransferase (AST)  $> 2.5$  times the upper limit of normal (ULN) (if no demonstrable liver metastases or  $> 5$  times ULN in the presence of liver metastases)
  - Total bilirubin  $> 1.5$  times ULN (if no liver metastases or  $> 3$  times ULN in the presence of liver metastases)
  - Creatinine  $> 1.5$  times ULN concurrent with creatinine clearance (CrCl)  $< 50 \text{ mL/min}$  (measured or calculated by Cockcroft and Gault equation. It gives priority to measured by Cockcroft and Gault more than calculated.)
8. Poorly controlled diabetes mellitus as defined by the investigator's assessment and/or glycosylated haemoglobin (HbA1c) reading  $> 6.5\%$  ( JDS scale) within 28 days prior to the first dose of MEDI-573

Date

9. Multiple primary cancers
10. History of other invasive malignancy within 5 years except for cervical carcinoma in situ, non-melanomatous carcinoma of the skin or ductal carcinoma in site of the breast that have been surgically cured, and completely resected intramucosal gastric carcinoma
11. Evidence of significant active infection requiring antimicrobial, antifungal, antiparasitic or antiviral therapy or for which other supportive care is given
12. History of allergy or reaction to any component of the MEDI-573 formulation or drugs with a similar chemical structure or class to MEDI-573
13. Previous medical history, or evidence, of an intercurrent illness that in the view of the investigators may compromise the safety of the patient in the study
14. Judgment by the investigator that the patient should not participate in the study if the patient is unlikely to comply with study procedures, restrictions and requirements
15. Involvement in the planning and conduct of the study (applies to both AstraZeneca staff or staff at the study site)

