## **6.3 Safety procedures**

### **6.3.1 Enrolment and screening**

At enrolment, each potential subject will provide informed consent prior to starting any study specific procedures (see Appendix D of this Clinical Study Protocol for Ethics and Regulatory Requirements).

Each potential subject is assigned a subject identification number (SID). The SID (XXXXXXXXYYY) consists of a 7-digit centre number (XXXXXXX) and a 3-digit serial number (YYY, starting with 001) issued by each study centre in order of informed consent taken. If a subject withdraws from the study, then the SID cannot be reused.

Demographic data and other characteristics will be recorded and will include date of birth, gender, race, alcohol consumption, smoking history and others. A standard medical, medication and surgical history will be obtained with review of the selection criteria with the patient.

Each subject will undergo screening (see [Table 5](#) and [Table 9](#)) during the 28 days prior to the first dose to confirm eligibility (see Sections [4.1](#) and [4.2](#)). Tumour assessments and other clinical data obtained as standard of care prior to consent may be used for the study provided the assessments prior to the first dose of study treatment. However, no invasive or study-specific screening assessments will be performed until consent is obtained.

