## **6.9 Anti-tumour activity**

### **6.9.1 Tumour assessments**

Tumour response will be assessed in all subjects with measurable and/or non-measurable disease at baseline.

RECIST ver1.1 will be used for measurable, non-measurable, target lesions and non-target lesions and the objective tumour response criteria in this study.

The preferred methods of assessment are CT or MRI performed on anatomical coverage to adequately define all areas of disease at baseline.

Baseline tumour assessments should be performed no more than 28 days before the start of study treatment. Following the baseline assessment, tumour burden will be assessed for all subjects by RECIST ver1.1 after start of study treatment (see [Table 5](#) and [Table 9](#)) until discontinuation of study treatment (subjects who discontinue the study treatment for reasons other than disease progression or initiation of alternative anticancer therapy will undergo Tumour assessment 3 months after the last dose of MEDI-573) or withdrawal of consent. The same methods of assessment and the same anatomical coverage should be used as per baseline at each subsequent follow-up assessment. Any other sites at which new disease is suspected should also be imaged appropriately.

If the investigator is in doubt as to whether progression has occurred, particularly with response to non-target lesions or the appearance of a new lesion, it is advisable to continue treatment and reassess the subject's status at the next scheduled assessment or sooner if clinically required.

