## **7.7 Calculation or derivation of tumour response variables**

The preliminary anti-tumour activity of MEDI-573 will be assessed based on the following variables: objective response rate (ORR), time to response (TTR), duration of response (DR), time to progression (TTP), and progression-free survival (PFS).

Categorisation of overall objective tumour response assessment will be based on the RECIST ver1.1: complete response (CR), partial response (PR), stable disease (SD) and progressive disease (PD) for all subjects with measurable disease at entry.

Response will be calculated in comparison to the baseline tumour measurements obtained before starting study treatment. Progression will be calculated in comparison to when the tumour burden was at a minimum (ie, smallest sum of diameters previously recorded since starting the study).

For patients that have measurable disease at entry, overall response at entry will be determined programmatically by the measurement of the target lesion, the response of the non-target

Date

lesion and the presence of new lesion according to the RECIST ver1.1. The subject's best overall response is the best response recorded from the start of the study treatment.

In the case of SD, measurements should have met the SD criteria at least once after the study start. To be assigned a status of partial response or complete response, changes in tumour assessments should be confirmed no less than 4 weeks after the criteria for response were first met.

For subjects that only have non-measurable disease at study entry, RECIST will be used. Visit response will be assigned programmatically and summarised separately.

Percentage change in tumour size will be determined by the percentage change in the sum of the longest diameters of target lesions.

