### **7.7.1 Objective response and disease control**

ORR is defined as the proportion of subjects with confirmed CR or confirmed PR according to RECIST ver1.1. Confirmed responses are those that persist on repeat imaging study  $\geq 4$  weeks after the initial documentation of response.

TTR will be measured from the start of treatment with MEDI-573 to the first documentation of objective response and will only be assessed in subjects who have achieved objective response.

DR will be defined as the duration from the first documentation of objective response to the first documented disease progression. DR will only be calculated for the subgroup of subjects with an objective response during the study period (until 3 months after the last dose).

TTP will be measured from the start of treatment with MEDI-573 until the documentation of disease progression during the study period (until 3 months after the last dose).

PFS will be measured from the start of treatment with MEDI-573 until the documentation of disease progression or death due to any cause, whichever occurs first during the study period (until 3 months after the last dose).

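### A lesion can receive palliative radiotherapy after its baseline scan and before the first dose, so radiotherapy shrinkage can count as MEDI-573 response

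*Protocol*

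**What the plan says.** Exclusion criterion 1 (Protocol, Section 4.2) sets washouts by type of earlier treatment. Radiotherapy is split in two: "Radiotherapy with a wide field of radiation within 4 weeks" of the first dose, or "radiotherapy with a limited field of radiation for palliation within 2 weeks of the first dose of MEDI-573". Chemotherapy, small-molecule targeted therapy and "hormonal therapy for cancer related treatment within 4 weeks of the first dose of MEDI-573" also carry 4 weeks, as does major surgery. Investigational agents carry 30 days. Biological therapies, and nitrosourea or mitomycin C, carry 6 weeks.

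Section 6.9.1 sets the age of the baseline scan: "Baseline tumour assessments should be performed no more than 28 days before the start of study treatment". Tables 5 and 9 give the same screening window, Day -28 to Day -1.

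Section 7.7 fixes the reference: "Response will be calculated in comparison to the baseline tumour measurements obtained before starting study treatment". Percentage change in tumour size is taken from the sum of target-lesion diameters, and progression from the smallest sum recorded. Section 7.7.1 adds: "ORR is defined as the proportion of subjects with confirmed CR or confirmed PR according to RECIST ver1.1".

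Inclusion criterion 6 asks for "At least one lesion (measurable and/or non-measurable) that can be accurately assessed at baseline" and suitable for repeated assessment. It sets no condition on irradiation.

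**The concern.** A baseline measurement should describe the tumour as it stands when study treatment begins. If another local treatment acts on a lesion between that measurement and the first dose, the later change mixes two effects. The protocol avoids this for every listed anticancer treatment except limited-field palliative radiotherapy.

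A site could scan on Day -28, irradiate a painful lesion between Day -25 and Day -16, and dose on Day 1, with every criterion met. That lesion could be a target lesion, or the only assessable one. Anti-tumour activity is a secondary objective (Section 1.2) of a single-arm study, so no control group would show that shrinkage came from radiotherapy.

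**Working it through.** **The plan's own figure.** Three cohorts of 3 to 6 evaluable subjects give 3 × 3 = 9 to 3 × 6 = 18, as Section 3.1 states. The point does not depend on this figure. It matters only for the weight of one response, below.

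**Window comparison.** Open interval = scan window (28 days, Section 6.9.1) minus washout (Section 4.2).

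| Earlier treatment | Washout (days) | 28 − washout |
|---|---|---|
| Limited-field palliative radiotherapy | 14 | 14 |
| Wide-field radiotherapy | 28 | 0 |
| Chemotherapy, targeted, hormonal therapy | 28 | 0 |
| Major surgery | 28 | 0 |
| Investigational agents | 30 | −2 |
| Biologicals | 42 | −14 |
| Nitrosourea, mitomycin C | 42 | −14 |

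Only the first row is positive. The 7-day limits on steroids and other immunosuppressives are not listed as anticancer treatment and are left out.

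**Permitted orderings.** If radiotherapy is allowed up to Day -15, a scan on Day -s (s = 16 to 28) can be followed by radiotherapy on s − 15 different days. The sum 1 + 2 + … + 13 gives 91 pairs of scan day and radiotherapy day. If Day -14 is also allowed, the sum 1 + … + 14 gives 105.

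**Does other text close the interval?**
- Section 6.9.1 does not require the scan to follow radiotherapy, does not bar an irradiated lesion as a target, and does not call for a new baseline.
- Section 4.3.1 prohibits anticancer drugs during the study and does not name radiotherapy.
- The tumour response set (Table 20) takes every dosed subject with a post-dose tumour assessment.
- Confirmation after at least 4 weeks (Section 7.7) does not help if the shrinkage persists.
- Exclusion criterion 3 covers brain metastases in part, through its 4-week condition.

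**Timing of the first on-treatment scan.** Scans precede odd cycles, so the first falls at about Day 43. Radiotherapy on Day -27 to Day -15 is then (42 + 27)/7 = 9.9 to (42 + 15)/7 = 8.1 weeks earlier.

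**Response, illustrated.** Assume a partial response needs a 30% fall in the sum. The protocol does not print this threshold. Two 30 mm target lesions give a sum of 60 mm. If the irradiated one shrinks to 10 mm and the other is unchanged, the sum is 40 mm: (40 − 60)/60 = −33.3%. In general, if the irradiated lesion carries a share w of the sum, it must shrink by 0.30/w:
- sole target lesion (w = 1): 30%;
- one of two equal lesions (w = 0.5): 60%;
- one of three equal lesions (w = 1/3): 90%;
- w below 0.30: it cannot produce a response alone.

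**Progression, illustrated in both directions.**
- Offset: the other lesion grows from 30 to 45 mm by the same scan. Without radiotherapy the sum is 75 mm (+25% on 60). With it the sum is 10 + 45 = 55 mm (−8.3%), and the growth is hidden at that scan.
- Earlier progression: the sum first falls to 40 mm, which becomes the nadir. A later 8 mm of growth is 8/40 = 20%, against 8/60 = 13.3% from an unaltered sum.

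**Weight of one spurious response.** 1/3 = 33.3 points, 1/6 = 16.7, 1/9 = 11.1, 1/18 = 5.6. These are illustrations only, since the denominators are DLT-evaluable counts.

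**The case against.** **RECIST may already deal with it.** Section 6.9.1 hands lesion handling to RECIST 1.1, which may restrict irradiated lesions. That guideline is not in hand, and the protocol writes out none of its lesion rules, so the interval cannot be taken as closed. If RECIST does restrict such lesions, the fix only makes the rule explicit for the site.

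**The analysis plan may handle it.** It could exclude affected lesions or assessments. But the choice of target lesions and the timing of the baseline scan are made at the site before dosing and belong in the protocol.

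**The example is chosen to succeed.** This stands. A 67% shrinkage of one of two targets has no source in the documents, and a palliated lesion may not be measurable at all. The table of shares above shows how much shrinkage is needed.

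**The stakes are modest.** This also stands. Activity is described as preliminary and summarised descriptively, and all data are listed, so an odd response can be examined individually.

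**Section 6.3.1.** A reader might infer that it widens the interval, because it says "Tumour assessments and other clinical data obtained as standard of care prior to consent may be used for the study" and the condition attached, which is incomplete as printed, names only the first dose. The documents do not support this. Section 6.9.1 limits all baseline tumour assessments to 28 days, the same paragraph of Section 6.3.1 opens with the 28-day screening period, and Tables 5 and 9 agree.

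**Conclusion.** The point holds on the protocol's own dates. For about 14 days, limited-field palliative radiotherapy can follow the baseline scan with every criterion met. The resulting shrinkage can then count in ORR, TTR and percentage change, and can offset growth in other target lesions when progression is assessed.

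Three stronger readings should not be drawn:
- That TTP and PFS are biased in the drug's favour. Offsetting hides growth, but a lower nadir brings later progression forward, so the net direction is not established.
- That ORR moves by 5.6 to 11.1 points. The 9 to 18 subjects are those evaluable for DLT. The ORR denominator comes from the tumour response set, which can include dosed subjects who were replaced, and Section 7.7 summarises subjects with only non-measurable disease separately.
- That the main conclusions are at risk. The primary objective is safety and tolerability, and escalation rests on DLTs.

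The conclusion assumes that no rule outside the visible text bars the lesion. How often such radiotherapy would occur is unknown. This is a cheap improvement to a descriptive secondary objective.

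**What to change.** In Section 6.9.1, with a cross-reference from inclusion criterion 6, state that a lesion irradiated after the baseline scan and before the first dose may not be a target lesion, nor the sole lesion used to meet inclusion criterion 6, unless a new baseline scan was taken after the last fraction. The radiotherapy washout is unchanged, and Section 6.3.1 needs no edit on this account. With this rule the open interval falls from 14 days to 0 for target lesions.

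The cost is one sentence and a cross-reference in an amendment. Usually no extra scan is needed, because the irradiated lesion is simply not chosen as a target. The exception is a rare patient whose only assessable lesion was just irradiated: that patient needs a repeat baseline scan or is not enrolled.

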### **4.3 Restrictions**

The following restrictions apply while the subject is receiving study treatment and for the specified times before and after:

1. Females of child-bearing potential should use reliable methods of contraception from the time of informed consent until 6 months after discontinuing study treatment. Acceptable methods of contraception include the use of oral contraceptives with an additional barrier method (since the investigational product may impair the effectiveness of oral contraceptives), double barrier methods (diaphragm with spermicidal gel or condoms with contraceptive foam), Depo-Provera, partner vasectomy, or total abstinence (see Section 8.3.1).
2. Male subjects should use barrier contraception and refrain from donating sperm from the start of dosing until 6 months after discontinuing study treatment. If male subjects wish to father children they should be advised to arrange for freezing of sperm samples prior to the start of MEDI-573 (see Section 8.3.2).

For restrictions relating to concomitant medications see next Section 4.3.1.

Date

#### 4.3.1 Concomitant treatments

All concomitant medications used by the subject from the time the subject signs the informed consent form through 30 days after the last dose of MEDI-573 will be recorded on source documentation.

Subjects may receive medications to treat AEs as deemed necessary by the investigators.

Any anticancer drug is not allowed during study.

Pre-medication will be allowed after, but not before the first dose of study treatment. This includes management of diarrhoea, nausea and vomiting.

Diphenhydramine and acetaminophen, or the institutional equivalents, may be administered for treatment of an infusion reaction during infusion or prophylactic administration for subjects who experience an infusion reaction. If Grade 2 or Grade 3 infusion reaction occurs and steroid is considered preferable to acetaminophen and diphenhydramine, steroid may be administered at the investigator's decision.

The routine use of ESAs and colony stimulating factors is not allowed. Use of such agents in the first cycle will require replacement of the subject in that cohort.

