#### **5.1.4 Definition of dose-limiting toxicity**

DLT will be graded according to the NCI CTCAE V4.0 and will be assessed from Cycle 1, Day 1 through Cycle 1, Day 21.

A DLT is defined as:

1. Any Grade 3 or higher non-haematologic toxicity that occurs during the DLT assessment period where a cause other than the investigational product cannot be reasonably justified with the following exceptions:
  - Grade <4 high glucose (fasting) with a duration of <24 hours after administration of MEDI-573
  - Grade 3 fever (in the absence of neutropenia) defined as >40.0°C (39.5°C in the axilla) that resolves to normal or baseline within 24 hours of treatment and is not considered an SAE
  - Grade 3 rigors/chills that respond to optimal therapy
  - Any isolated or transient laboratory changes without associated clinical signs or symptoms.
2. Any Grade 3 or higher haematologic toxicity that occurs during the DLT assessment period where a cause other than the investigational product cannot be reasonably justified.

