#### **5.1.6 Definition of evaluable subject**

Subjects are considered evaluable if they receive MEDI-573 and either:

Date

- have received 3 doses of MEDI-573 (Cohorts 1 or 2) or 1 dose of MEDI-573 (Cohort 3) during the cycle and are followed for 21 days from the date of first dose (one cycle)
- have experienced a DLT during the cycle 1

Subjects who have a delay in drug administration during the DLT evaluation period are considered as unevaluable.

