### **5.1.7 Dose escalation committee**

The DEC will evaluate the safety and tolerability of MEDI-573 collected in the cohort and decide on whether to proceed to dose escalation for the next cohort.

The DEC will consist of:

- Study Team Physician, who will chair the committee, or delegate
- Principal Investigator or representative(s) of the study sites

Sub Investigator from investigational sites, the Study Pharmacokineticist, Study Statistician, Patient Safety Scientist and Study Delivery Team Leader may also be invited as appropriate. The DEC remit document for this study will define the exact membership and who should be present for decisions to be made.

Once there are at least 3 evaluable subjects at a dose level, the DEC will review and assess all available safety data documented by the investigators, if possible, together with available PK data, such as demography, AEs of CTCAE grade  $\geq 2$  observed in the DLT assessment period (Days 1 to 21 in Cycle 1), and whether the beginning of Cycle 2 for MEDI-573 has to be postponed or not, to make a decision on for the next cohort of subjects. Any dose interruptions will be taken into account.

The decision may be to:

1. Proceed with dose escalation – refer to Section [5.1.3](#)
2. Expand the cohort to a maximum of 6 evaluable subjects
3. Stop the dose escalation part of the study

Any subject started on treatment in error, as he/she failed to comply with all of the selection criteria but meets the criteria of an evaluable subject, will be reviewed on a case by case basis by the DEC to determine if the subject should be included or excluded in the decision for dose escalation.

The decisions and decision-making of the DEC on the next dose level will be documented and give a notice to the principal investigators prior to dosing any new subjects.

Date

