**Table 20**                      **Analysis sets**

Analysis Set	Definition
Safety	All subjects who received at least 1 dose of MEDI-573.
MTD	All subjects who have received at least 1 full cycle of MEDI-573 and completed the safety follow-up through the DLT evaluation period, or who experienced a DLT.
PK	All subjects who received at least 1 dose of MEDI-573 and for whom an adequate PK profile has been obtained.
Pharmacodynamics	All subjects who received at least 1 dose of MEDI-573 with any post-pharmacodynamics data
Tumour response	All subjects who have received at least 1 dose of MEDI-573 and at least one tumour assessment after the initiation of MEDI-573.
Exploratory biomarkers	All subjects who received at least 1 dose of MEDI-573 and have biomarkers data.

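### Two Cycle 1 rules (replacement after ESA or colony-stimulating factor use, unevaluable after a dose delay) make no exception for a subject with a DLT and contradict the rule that such a subject is evaluable

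*Protocol*

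**What the plan says.** Two provisions take subjects out of the count, with no reference to DLT status:

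- Section 4.3.1 bars routine use of ESAs and colony-stimulating factors, then adds: "Use of such agents in the first cycle will require replacement of the subject in that cohort".
- The closing sentence of Section 5.1.6 reads: "Subjects who have a delay in drug administration during the DLT evaluation period are considered as unevaluable".

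Other provisions keep a subject with a DLT in:

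- The second bullet of Section 5.1.6 makes subjects evaluable if they "have experienced a DLT during the cycle 1".
- The MTD set in Table 20 is "All subjects who have received at least 1 full cycle of MEDI-573 and completed the safety follow-up through the DLT evaluation period", and its definition then adds anyone who experienced a DLT.
- The stop rule in Section 5.1.3 counts subjects with a DLT without requiring that they be evaluable. Section 5.1.5 states the same two-or-more rule among evaluable subjects only.

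The link to the outcome comes from Section 5.1.4, item 2. Where no other cause can reasonably be justified, it counts as a DLT "Any Grade 3 or higher haematologic toxicity that occurs during the DLT assessment period". Section 4.3.1 also allows treatment of such an event: "Subjects may receive medications to treat AEs as deemed necessary by the investigators".

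**The concern.** Under Section 5.1.3 the decisions to escalate rest on evaluable subjects: none with a DLT among 3, or one among 6. Who is evaluable therefore decides the result. ESAs and colony-stimulating factors act on blood counts, and a Grade 3 or higher haematologic toxicity is itself a DLT, so the replacement trigger in Section 4.3.1 is tied to the event being counted. The delay rule may be too, since an adverse event is an obvious reason for a late dose.

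A subject removed because of a toxicity and replaced by a new subject lowers the observed DLT count and never raises it. At stake are the decision to open the next dose level, the MTD if one is reached, and agreement between the escalation count and the DLT count later reported in the MTD set.

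**Working it through.** **The passages side by side**

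| Subject in Cycle 1 | 5.1.6, bullet 2 | Table 20, MTD set | 4.3.1 or last sentence of 5.1.6 |
|---|---|---|---|
| DLT, then ESA or colony-stimulating factor | evaluable | included | must be replaced (4.3.1) |
| DLT and a delayed dose (Cohorts 1 and 2) | evaluable | included | unevaluable (5.1.6) |

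Each row has two answers. Section 5.4.1 ties replacement to subjects who are withdrawn and not evaluable, which suggests that a replaced subject leaves the count. The delay row is essentially empty for Cohort 3, which has a single Cycle 1 dose on Day 1.

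**Effect on one cohort (no assumption about rates needed)**

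If the replacement subject has no DLT:
- 1/3 (expand to 6) becomes 0/3 (escalation may occur).
- 2/6 (dose not tolerated) becomes 1/6 (escalation may occur).

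**The plan's own figures**

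Three cohorts of 3 to 6 give 3 × 3 = 9 and 3 × 6 = 18, matching the 9 to 18 evaluable subjects in Section 3.1. The protocol states no operating characteristics for its 3+3 rule.

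**Illustration of size**

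Let p be the true DLT probability and q the share of DLT subjects removed and replaced. Both are assumptions; the protocol gives neither.

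- P(dose passes) = (1−p)³ + 3p(1−p)² × (1−p)³ = (1−p)³ + 3p(1−p)⁵
- DLT rate among counted subjects: p′ = p(1−q)/(1−pq), put into the same formula

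At p = 0.30:
- q = 0: 0.343 + 0.9 × 0.168 = 0.49
- q = 0.10: p′ = 0.27/0.97 = 0.278; 0.376 + 0.163 = 0.54
- q = 0.25: p′ = 0.225/0.925 = 0.243; 0.433 + 0.181 = 0.61
- q = 0.50: p′ = 0.15/0.85 = 0.176; 0.559 + 0.201 = 0.76

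Probability of passing at other assumed rates:

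| p | q = 0 | q = 0.10 | q = 0.25 | q = 0.50 |
|---|---|---|---|---|
| 0.20 | 0.709 | 0.744 | 0.798 | 0.887 |
| 0.40 | 0.309 | 0.351 | 0.428 | 0.600 |
| 0.50 | 0.172 | 0.203 | 0.265 | 0.428 |

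Simulation with 200,000 runs per setting agreed with the formula where checked (p = 0.50: 0.264 at q = 0.25 and 0.428 at q = 0.50).

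**The case against.** The best defence is that the protocol already means every DLT to count. The DLT bullet in Section 5.1.6 is specific, Table 20 agrees with it, and the Section 5.1.3 stop rule speaks of subjects rather than evaluable subjects. On that view only a precedence clause is missing. Section 4.3.1 may also be aimed at routine use that could mask toxicity, and replacing a subject need not erase an event already seen. For the delay rule, Section 5.1.8 forbids Cycle 1 delays and Section 5.4.1 lists a DLT as a ground for discontinuation, so a DLT combined with a delayed dose should be uncommon. The DEC reviews all available safety data and would see the event.

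Most of this stands as a limit on frequency and size. It does not remove the contradiction. The replacement sentence in Section 4.3.1 is mandatory and names the agents without restricting the reason for use. Section 5.1.6 provides for delays even though they are forbidden. The difference between Sections 5.1.3 and 5.1.5 leaves it open which count governs.

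A reader might infer that DEC discretion is a third rule of the same kind. The text does not support that. In Section 5.1.7 the case "will be reviewed on a case by case basis by the DEC to determine if the subject should be included or excluded" only if the subject was started in error and meets the evaluable definition. That presupposes Section 5.1.6 and does not contradict it. Nor does it conflict with the no-replacement sentence in Section 5.4.1, which concerns withdrawn subjects. It remains a weak choice, because a subject with a DLT could be excluded after the outcome is known.

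**Conclusion.** The protocol is wrong as written: Section 4.3.1 and the last sentence of Section 5.1.6 contradict the DLT bullet of Section 5.1.6 and the MTD set, and nothing ranks them. Applied literally, they allow outcome-dependent removal that can reverse an escalation decision in a cohort of 3 to 6, always towards calling the dose tolerated.

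A reader might go further and conclude that the protocol instructs sites to discard DLTs, or that the bias has a known size. Neither follows. Several passages point towards counting the DLT, and the probabilities above depend wholly on assumed p and q. A removal share of 25% or 50% of all DLTs is illustrative: the growth-factor route reaches only haematologic DLTs treated with these agents, and the delay route only Cohorts 1 and 2. Section 2.2.2 reports no DLT among 25 subjects in the US study, but those are pooled over doses, with one subject at 30 mg/kg.

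**What to change.** Reconcile the passages with one definition:

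1. In Sections 4.3.1 and 5.1.6, state that a subject with a Cycle 1 DLT remains evaluable, counts as a DLT and is not replaced, regardless of ESA or colony-stimulating factor use or any dose delay.
2. Use that definition in Sections 5.1.3 and 5.1.5 and for the MTD set in Table 20, so that the stop rule, the MTD and the reported DLT count share one numerator and one denominator.
3. As a secondary recommendation, add to Section 5.1.7 that case-by-case exclusion of a subject started in error does not remove an observed DLT from the count.

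The cost is a few sentences in an amendment and a matching line in the DEC remit. The change concerns evaluability only and alters no dose, treatment or supportive-care rule. The downside is that an occasional DLT of doubtful attribution will count against a dose.
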